3.3. Design and Outcomes

This project will use a randomized design to compare treatment satisfaction and effectiveness of Contingency Management (CM) and Brief Motivational Intervention + Substance Free Activities Session + Mindfulness-Based Adherence Promotion (BSM) for medication adherence in patients who are initiating buprenorphine-naloxone treatment at our Center for Addiction Science (N=40). The interventions will take place across the first 4 physician visits of buprenorphine-naloxone treatment, starting after treatment intake.

Primary outcomes will include feasibility and satisfaction at the fourth weekly intervention visit, and an efficacy comparison of intervention group differences in buprenorphine-naloxone treatment adherence, defined as (1) attendance at physician visit AND (2) buprenorphine-naloxone presence in urine toxicology.

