3.4. Duration

3.4.1. CM Group Course and Session Duration

Participants assigned to the CM arm will have contact with study staff at their first physician visit (intake visit at the Center for Addiction Science) and then at the following 4 physician visits that are scheduled as a regular buprenorphine-naloxone treatment course. These visits are often scheduled at 1 week, 2 weeks, 4 weeks, and 8 weeks following intake (see Figure 1). However, this varies with some patients, thus participation could potentially last 4 months as a result of them being seen on a monthly basis. Participation at each intervention session is expected to last for 10minutes for the assessment and 2 minutes for the intervention (“number wheel” gift card picker).

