8.5 Session Windows

Following the Baseline Visit, participants will complete 4 sessions in no greater than 30-day increments. These visits will be referred to as Session 1 (S1), Session 2 (S2), Session 3 (S3), Session 4 (S4). The window scheduling guidelines for sessions are as follow:

- S1 opens when their 1st physician return visit is scheduled.
- S1 closes the day before their S2 is scheduled OR at 30 days from S1 window open.
- S2 opens when their 2nd physician return visit is scheduled or the day after S1 window closes (e.g. if S1 is not completed in order to keep under the 30 day maximum).
- S2 closes the day before their S3 is scheduled OR at 30 days from S2 window open.
- S3 opens when their 3rd physician return visit is scheduled or the day after S2 window closes.
- S3 closes the day before their S4 is scheduled OR at 30 days from S3 window open.
- S4 opens when their 4th physician return visit is scheduled or the day after S3 window closes.
- S4 closes 4 weeks from S4 window open (but continue to try to assess).

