12. MEASURES

12.1. Table 1. List of Measures

Measure	Time to Complete (minutes)	Baseline	1,2, 4, and 8 week sessions	8 week blind	Medical Chart at 30 days
Contact Information	1	X			
Referral source (how did they get to the CAS)?	<1	X			
Screening Questionnaire	<1	X			
Exclusion reason (if applicable)	n/a				
Demographics (gender/race/ethnicity/education/zip code/insurance)	3	X			
Opioid Use Disorder (Diagnostic and Statistical Manual of Mental Disorders-5) ⁹³ interview	1	X			
Attended first physician visit	n/a		X		
Attended second physician visit	n/a		X		
Attended third physician visit	n/a		X		
Attended fourth physician visit	n/a		X		
Number of treatment visits attended (allow for drop out, drop back in): CUMULATIVE ADHERENCE	n/a				X
Urine Toxicology (buprenorphine and all other substances)	n/a	X	X		X
Timeline followback on alcohol, substance use, and opioid use	3	X	X		
Delay Discounting ⁵⁸	2	X		X	
Opioid Purchase Task ⁴⁶	1	X	X		
Engagement in Substance Free Activities ⁵⁴	2	X		X	
Time Spent On Activities	2	X			
Opioid Craving Symptoms ⁹⁵ (Opioid Cravings Scale)	1	X	X		
Buprenorphine-Naloxone dose log (did you miss any days?)	<1		X		
Dosage of Buprenorphine-Naloxone Prescribed (obtained from medical record at each session)	n/a	X	X		X
Treatment Satisfaction	4			X	
Prescription Drug Monitoring data	n/a	X	X		X
PEG for Chronic pain (3 items)	<1	X	X		
EQ5D5L (6 items) Quality of life for cost-effectiveness analyses	3	X		X	
PHQ-2 depression 2 items	<1	X	X		
GAD 2 anxiety 2 items only (also a 7 item version)	<1	X	X		
Treatment history (times in treatment, medication used)	<1	X			
Economy Contribution (3 items)	<1	X	X		
If dropped out: Are you receiving but (or opioid replacement) treatment somewhere else?	<1		X		
Adverse Events	<1		X		
Participant time to complete all measures at sessions:		20.5	11	10	n/a

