Statistical Analysis Plan: SMART Project 3 (Efficacy Study)

Because these analyses will focus on determining and intervention feasibility and satisfaction, and preliminary intervention effect sizes (with less concern focused on testing for statistical significance), outcome analyses will be conducted using a separate analysis for each outcome at each follow up observation. To compare groups, baseline and follow up variables will be entered into a 5 (baseline vs. follow ups at 1, 2, 3, and 4 weeks) by 2 (CM vs. BSM) analysis of variance (ANOVA) which will yield effect sizes for time, and interactions of time by intervention. The primary dependent variables will be attendance at physician visits, saliva drug screen data (positive for buprenorphine and negative for illicit opioids), and prescription drug monitoring. We hypothesize that a greater number of CM participants will demonstrate adherence to buprenorphine-naloxone than BSM, but that those randomized to BSM will report increased time allocated to substance-free activities, decreased delayed reward discounting, and demand for opioid.

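### The SAP's time factor (baseline and weeks 1 to 4) matches neither the protocol's return visits (usually weeks 1, 2, 4 and 8) nor the occasions on which several outcomes are measured

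*SAP*

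**What the plan says.** The SAP gives one model for comparing groups: a "5 (baseline vs. follow ups at 1, 2, 3, and 4 weeks) by 2 (CM vs. BSM) analysis of variance", "which will yield effect sizes for time, and interactions of time by intervention". An earlier sentence of the same paragraph says that "outcome analyses will be conducted using a separate analysis for each outcome at each follow up observation". It does not say what is to be estimated there, or how that fits with the five-level model.

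On visit timing, protocol section 3.4.1 says of the physician visits to which the sessions are tied: "These visits are often scheduled at 1 week, 2 weeks, 4 weeks, and 8 weeks following intake". Section 3.4.2 says the same for the BSM arm. Both sections add that timing varies and that "participation could potentially last 4 months as a result of them being seen on a monthly basis". Section 8.5 defines the sessions by return visit and says that "participants will complete 4 sessions in no greater than 30-day increments". Table 1 (section 12.1) heads its session column "1,2, 4, and 8 week sessions" and has a separate column for a blinded assessment at 8 weeks.

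One protocol sentence leans towards the SAP's timing. Section 3.3 reads: "Primary outcomes will include feasibility and satisfaction at the fourth weekly intervention visit".

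Sections 3.4.4 and 3.6.4 add a chart review 30 days after Session 4, expressly for efficacy. The SAP does not mention it.

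**The concern.** There are two problems.

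The first is the time axis. A time-by-arm effect size is interpretable only if the reader knows when each level was observed, and here the SAP and the protocol disagree on that. The SAP's stated purpose is to produce preliminary effect sizes, so an adherence difference attached to the wrong point in treatment is a reporting error in the main product of the pilot.

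The second is the match between model and data. A five-level time factor with an interaction presupposes a baseline value and four follow-up values. Table 1 shows that several outcomes do not have them. These include satisfaction, which section 3.3 makes primary and the SAP names as a focus, and adherence, which is the efficacy outcome. An analyst would have to decide after the fact which levels to drop and what to estimate instead.

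**Working it through.** **Step 1: compare the two sets of weeks (baseline = 0).**

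- SAP: {0, 1, 2, 3, 4}
- Protocol, usual schedule: {0, 1, 2, 4, 8}
- Common: {0, 1, 2, 4}. SAP only: {3}. Protocol only: {8}.

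The number of occasions does agree: baseline plus four sessions makes five. The weeks do not.

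**Step 2: apply each reading of the SAP to a patient on the usual schedule.**

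- Calendar weeks: three of the four sessions (weeks 1, 2 and 4) fall within the SAP's range. Week 3 has no scheduled visit, and Session 4 is left out.
- Visit number: all four sessions are used. The third visit, usually at 4 × 7 = 28 days, is labelled week 3 (21 days). The fourth, usually at 8 × 7 = 56 days, is labelled week 4 (28 days), half its usual time. For a patient seen monthly, taking 30-day months, the fourth visit is at 4 × 30 = 120 days.

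**Step 3: count the levels that each outcome can fill.** The inputs are the columns marked in Table 1. Time is indexed by protocol occasion, and the 8-week blinded assessment is treated as the same level as Session 4. With k occasions and two arms, an outcome fills 2k of the 10 arm-by-time cells. It leaves k − 1 degrees of freedom for time and (k − 1)(2 − 1) = k − 1 for time by arm. The SAP's model assumes k = 5, so 4 of each.

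| Outcome | Occasions in Table 1 | k | Cells of 10 | df for time, and for time by arm |
|---|---|---|---|---|
| Buprenorphine in urine; prescription monitoring; opioid purchase task | Baseline, Sessions 1 to 4 | 5 | 10 | 4 |
| Attendance, hence the adherence composite | Sessions 1 to 4 | 4 | 8 | 3 |
| Delay discounting | Baseline, 8-week blinded assessment | 2 | 4 | 1 |
| Satisfaction | 8-week blinded assessment | 1 | 2 | 0 |

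The model as written therefore fits the first row only. For satisfaction, neither of the effects that the SAP says the model will yield can be estimated. Delay discounting supports a two-by-two version. Attendance has no baseline entry, and because adherence requires attendance together with buprenorphine in urine (section 3.3), the composite has none either.

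**Step 4: look for occasions that the model leaves out.** Table 1 has a 30-day chart column marked for urine toxicology, prescription monitoring and the cumulative count of visits attended. None of the SAP's five levels corresponds to it.

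**The case against.** The strongest defence is that the SAP's weeks are loose shorthand for visits 1 to 4. Five levels is the right count, section 8.5 defines sessions by return visit, and the forms in sections 12.2.7 to 12.2.10 record adherence by first, second, third and fourth visit. On that reading no observation is lost and no effect size changes; only the labels are wrong. This stands, and the visit-number reading is the more plausible one. A reader might infer that Session 4 data would be discarded. That follows only from the calendar reading, and the documents do not establish that it is intended.

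A second defence is that the SAP's provision for a separate analysis of each outcome at each follow-up covers satisfaction, since one observation leads naturally to one between-arm comparison. This also stands in part. A reader might infer that satisfaction cannot be analysed at all, and the SAP does not support that. It is also fair to say that satisfaction is primary in section 3.3 but is not among the SAP's primary dependent variables. What remains is that the provision names no estimate, and the paragraph does not say which outcomes follow it and which follow the five-by-two model.

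A third defence is that monthly patients may be few. Section 7 requires physician confirmation of a regular initiation schedule, and section 3.5.2 expects about 5% of new patients to depart from the regular course. That limits the 120-day case. It does not affect the mismatch for patients on the usual schedule.

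**Conclusion.** The inconsistency is real and should be fixed. One of the SAP's five weeks has no counterpart in the usual schedule, and the usual week of Session 4 is not in the SAP. On the likelier reading, the last visit would be reported at half its usual time from intake. Separately, the five-level model does not match satisfaction (1 of 5 levels), delay discounting (2 of 5), or attendance and adherence (4 of 5, with no baseline), and it leaves out the 30-day chart review designated for efficacy.

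Two assumptions carry this: the 1, 2, 4 and 8 week pattern, which the protocol describes as frequent and not fixed, and the columns marked in Table 1.

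Two further inferences are tempting and not supported. One is a numerical error in reported retention or adherence: the documents give no drop-out rate, so none can be calculated. The other is that a mislabelled result would feed into the later trial: section 3.2 says only that Project 4 follows once feasibility, satisfaction and efficacy have been obtained. No sample size or power figure is affected.

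**What to change.** Reconcile the timing statements, and make the analysis follow sessions so that it holds whatever the patient's clinic schedule.

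- **SAP, time factor:** replace the four week-numbered follow-ups with *Sessions 1 to 4 (return visits, usually 1, 2, 4 and 8 weeks after intake)*. Report actual days from intake at each session, by arm.
- **Protocol section 3.3:** replace the reference to a fourth weekly visit with *Session 4 (usually week 8)*.
- **SAP, occasions and estimate for each outcome:**
  - Satisfaction: between-arm difference with a 95% confidence interval at its single time point.
  - Delay discounting: between-arm difference at the 8-week blinded assessment, adjusted for the baseline value.
  - Attendance and adherence: the four return visits, with no baseline level, and the 30-day chart review reported separately.
  - Five-level model: only for outcomes collected at baseline and at every session.
- **SAP, separate-analysis sentence:** say which outcomes it governs, so that it no longer competes with the five-by-two model.

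The confidence interval and the baseline adjustment are recommended choices; the documents do not require them. The cost is wording in the SAP and one sentence of section 3.3, with no new data, visits or participants.

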7. ELIGIBILITY CRITERIA

Participants must meet the following eligibility criteria to participate in this study:

- Present for an appointment at CAS or ARC for buprenorphine-naloxone treatment of OUD
- Be eligible for buprenorphine-naloxone treatment (e.g., Suboxone, Bunavail, Zubsolv) as determined by [name]
- At least 18 years of age or older
- Access to a telephone
- Ability to understand consent procedures
- Physician confirmation of a "regular" initiation visit schedule (to ensure completion within pilot study window)

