12.2.11. Cumulative Adherence

Number of treatment visits attended (allow for drop out, drop back in)	Filemaker calculation
--	-----------------------

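### The SAP's adherence comparison, a 5×2 ANOVA listing only time and time-by-arm effects, does not target the CM–BSM difference, and no arm contrast is named as the main one

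*SAP*

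**What the plan says.** Protocol section 3.3 lists among the primary outcomes "an efficacy comparison of intervention group differences in buprenorphine-naloxone treatment adherence". It defines adherence as a composite: the physician visit was attended and buprenorphine was found in urine. Sections 12.2.7 to 12.2.10 score this composite yes or no at each of follow-up visits 1 to 4.

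The SAP is one paragraph. It aims at early estimates of intervention effect rather than at significance tests, and contains four relevant statements:

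- **Per-visit analyses:** "outcome analyses will be conducted using a separate analysis for each outcome at each follow up observation".
- **Group comparison:** the layout is "5 (baseline vs. follow ups at 1, 2, 3, and 4 weeks) by 2 (CM vs. BSM", and the analysis is an "analysis of variance (ANOVA) which will yield effect sizes for time, and interactions of time by intervention".
- **Variables:** the primary dependent variables are attendance, "saliva drug screen data (positive for buprenorphine and negative for illicit opioids), and prescription drug monitoring", listed separately.
- **Hypothesis:** "We hypothesize that a greater number of CM participants will demonstrate adherence to buprenorphine-naloxone than BSM".

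Neither document names an effect measure (risk difference, odds ratio or other) or a main visit for adherence. Protocol section 12.2.11 defines a per-participant count, "Number of treatment visits attended (allow for drop out, drop back in", but it counts attendance only and the SAP does not use it.

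**The concern.** The question is which arm is more adherent, and by how much. The two effects that the SAP lists do not answer it. A time effect pools the arms, and an omnibus interaction says only that the arm difference is not constant over occasions.

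The arm contrasts that would answer it are obtainable but not designated. With three SAP variables and four visits there are 3 × 4 = 12 per-visit contrasts, plus an arm row in each ANOVA. An analyst could choose among them after seeing the data. Effect estimates are the stated purpose of this pilot, and Protocol section 3.2 makes Project 4 follow once efficacy has been shown, so the choice matters.

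Two further features weaken the listed analysis. Attendance has no informative baseline, and the SAP's variables are not the composite on which the protocol bases the comparison.

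**Working it through.** The documents give no adherence rates, correlations, effect size or power calculation, so there is no figure of the plan to reproduce. The inputs from the documents are 20 participants per arm (Protocol 3.5), five occasions by two arms (SAP) and four scored visits (Protocol 12.2.7 to 12.2.10). All rates and correlations below are assumptions.

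**1. Where a CM–BSM difference falls in the ANOVA.** Let d be the arm difference at each of K occasions. The share of the between-arm sum of squares in the interaction is 1 − K × mean(d)² / Σd².

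- Steady 20 points, no baseline level: 1 − 4 × 400/1600 = 0. The listed effects miss all of it.
- Steady 20 points, baseline attendance entered as 1, so d = (0, 20, 20, 20, 20): mean 16, and 1 − 5 × 256/1600 = 0.20. The listed interaction misses 80%.
- d = (0, 10, 15, 20, 25): 1 − 5 × 196/1350 = 0.27.
- d = (0, 5, 15, 25, 35): 1 − 5 × 256/2100 = 0.39.
- d = (0, 0, 10, 20, 30): 1 − 5 × 144/1400 = 0.49.

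**2. No direction.** The interaction has (5 − 1)(2 − 1) = 4 degrees of freedom. Its sum of squares is unchanged when d becomes −d, so exchanging the arms leaves it the same. The pattern 35, 25, 15, 5 also gives 0.39, although the advantage shrinks instead of growing.

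**3. Baseline attendance.** Table 1 (Protocol 12.1) marks the attendance rows at the sessions only. Entry requires that a patient "Present for an appointment at CAS or ARC for buprenorphine-naloxone treatment of OUD", and the screening questionnaire (12.2.3) asks about the intake visit.

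- If baseline attendance is not collected, the fifth level does not exist and the five-level ANOVA cannot be run for attendance.
- If it is entered as 1, take identical arms at a flat 70%. The occasion means are 1, 0.7, 0.7, 0.7, 0.7, with overall mean 0.76. The time sum of squares is 40 × (0.24² + 4 × 0.06²) = 40 × 0.072 = 2.88, although nothing changes after baseline.
- Each participant's five-level mean is then (1 + 4p)/5, where p is the proportion over visits 1 to 4. A 20-point difference becomes 0.8 × 20 = 16 points. The rescaling is the same for everyone, so the arm F test is unchanged.

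**4. Illustration at 20 per arm.** This used 10,000 simulated trials per scenario and correlated binary visits with latent correlation 0.3 to 0.5. Values are mean partial eta-squared.

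| Scenario | Time | Interaction | Arm (not listed) |
|---|---|---|---|
| 80% vs 60% at all visits, baseline = 1 | 0.139–0.152 | 0.040–0.042 | 0.115–0.137 |
| 80% vs 75, 65, 55, 45%, baseline = 1 | – | 0.063–0.067 | 0.121–0.141 |
| 80% vs 60%, no baseline level | – | 0.026 | 0.116–0.137 |
| Identical arms, flat 70%, baseline = 1 | 0.134–0.147 | – | – |
| Identical arms, flat 70%, no baseline level | 0.026 | – | – |

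With no true effect, the interaction and arm values both average about 0.026.

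**5. Precision of a named estimate.** For one visit at 80% vs 60%, the 95% half-width is 1.96 × √((0.16 + 0.24)/20) = 0.277, about 28 points. For the proportion of four visits, the simulated mean half-width (t, 38 degrees of freedom) is 0.177 at latent correlation 0.3 and 0.199 at 0.5, about 18 to 20 points. The variance of that proportion is p(1 − p)(1 + 3φ)/4, where φ is the correlation between visits. At φ = 1 this equals p(1 − p), and the gain is gone.

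**6. Variables side by side.** The SAP has attendance, a saliva screen that must also be negative for illicit opioids, and prescription monitoring. The protocol has attended and buprenorphine in urine. Table 1 lists urine toxicology and no saliva test. Neither document says which definition carries the group comparison.

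**The case against.** The strongest reply is that the SAP does allow a comparison of the arms. The per-visit analyses come first in the paragraph and would naturally give signed differences, any ANOVA table includes an arm row, and the hypothesis states a direction. This stands. A reader might infer that the plan contains no arm comparison at all, and the documents do not support that. What remains is that no contrast or metric is designated as the main one.

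Time-by-arm is also a customary effect when outcomes have a real baseline. That is fair for delay discounting or urine toxicology, which Table 1 marks at baseline. The baseline point here concerns attendance, and the composite that contains it, not the drug screen.

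Nothing says that attendance is entered as 1 at baseline, and the SAP's mention of baseline variables may be generic. So the 20% to 49% shares, the 0.8 shrinkage and the built-in time effect hold only on that reading. On the other reading the level is absent, and the interaction captures none of a steady difference.

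The table may also tempt a reader to say that the arm effect is about three times the interaction and to take this as the amount missed. The two quantities use different error terms, depend on the assumed correlation and both include null bias, so the ratio should not be used that way.

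Finally, this is a pilot of 40 with little stress on significance. That limits the severity, but an aim of estimation makes a defined estimate more necessary.

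**Conclusion.** The concern holds as a mismatch between the primary efficacy question and the analysis that the SAP sets up to answer it. It should be fixed, but no stated figure is wrong. The absence of direction, and the loss of a steady difference (all of it without a baseline level, 80% with baseline attendance at 1), follow from the ANOVA algebra and do not depend on the assumed rates. The shares for changing differences depend on the assumed pattern. The eta-squared values and interval widths are illustrations under assumed rates and correlations.

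A reader might conclude that entering baseline attendance as 1 invalidates the arm test. It does not: only the raw marginal difference shrinks. The baseline value of 1 is itself inferred from eligibility and not stated.

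**What to change.** Rewrite the SAP paragraph as follows.

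- **Main estimate:** the CM–BSM difference, with 95% CI, in the proportion of physician visits 1 to 4 that were adherent, in all randomised participants. Use the urine-based composite of Protocol 12.2.7 to 12.2.10, with a missed visit counted as non-adherent. This is one defensible summary, and it gives one signed number.
- **30-day chart review:** Protocol 3.4.4 and 3.6.4 tie it to efficacy. State that it is a separate supportive efficacy outcome. Reconcile its starting point, which differs between the two sections only for participants who do not complete session 4.
- **Variables:** replace saliva with the urine screen actually collected. Keep attendance, the drug screen (including negative for illicit opioids) and prescription monitoring as further outcomes.
- **Time:** drop the baseline level for attendance and the composite, and index time by visit number. Reconcile the SAP's weeks 1 to 4 with the protocol's usual weeks 1, 2, 4 and 8, which the protocol says vary.
- **Status:** label the per-visit and ANOVA results supportive.
- **Late visits:** sections 12.2.7 to 12.2.10 score attendance at the scheduled day and time, while 8.5.1, 8.5.2 and 8.10 (Option for Scheduling) provide for a later visit within the window. State how such a visit is scored, and report the other scoring as a sensitivity analysis.

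No new data are needed. The baseline-to-follow-up time effect for attendance is lost. The gain in precision over a single visit is smaller if adherence persists more strongly within participants than assumed.

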3.5. Sample Size and Population

Approximately 40 participants will be recruited from UTHSC's Center for Addiction Science (CAS) for this study. We will randomize 20 participants to the CM group, and 20 participants to the BSM group.

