3.5.1. Randomization

Participants are individually assigned to a study arm by block randomization (1:1 allocation, block length of 4).

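### For continuous measures with a baseline value, the SAP reads the arm effect from the time-by-intervention interaction; adjusting for baseline would be more precise at almost no cost.

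*SAP*

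**What the plan says.** The SAP is a single paragraph. It states that "baseline and follow up variables will be entered into a 5 (baseline vs. follow ups at 1, 2, 3, and 4 weeks) by 2 (CM" versus BSM) ANOVA, so baseline is one of five levels of the time factor. The output is described as "analysis of variance (ANOVA) which will yield effect sizes for time, and interactions of time by intervention". It names no arm main effect, baseline covariate or other adjustment, and the Protocol has no analysis section that adds one. The same paragraph says that "outcome analyses will be conducted using a separate analysis for each outcome at each follow up observation".

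The stated aim is "preliminary intervention effect sizes (with less concern focused on testing for statistical significance". One hypothesis is that "those randomized to BSM will report increased time allocated to substance-free activities, decreased delayed reward discounting, and demand for opioid".

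Protocol section 3.5 gives the size: "We will randomize 20 participants to the CM group, and 20 participants to the BSM group". Section 3.5.1 specifies "block randomization (1:1 allocation, block length of 4".

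Table 1 (Protocol section 12.1) gives the schedule:
- **Baseline and the 8-week blinded call:** delay discounting, substance-free activities, EQ-5D-5L.
- **Baseline and each session:** opioid purchase task, craving.
- **Baseline only:** Time Spent On Activities.
- **No baseline value:** attendance, treatment satisfaction.

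**The concern.** In a randomised comparison, the participant's own baseline value is usually the best available predictor of the follow-up value. Used as a covariate, it removes variance that has nothing to do with treatment. Used as another level of the outcome, it is subtracted in full, and its own noise enters the estimate.

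With 20 per arm, chance baseline differences are not small. Under equal SDs only a fraction r of such a difference carries through to follow-up on average, where r is the baseline-to-follow-up correlation. The change score subtracts all of it.

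This pilot is meant to deliver effect sizes ahead of the next trial, so the width of the interval around each effect is the main thing its analysis can improve. Discounting and opioid demand are also effects that the SAP hypothesises for BSM.

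**Working it through.** The documents contain no power or precision calculation, so there is no stated figure to reproduce.

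**Inputs.** n = 20 per arm (Protocol 3.5). Correlation r between baseline and follow-up: not given, assumed 0.3 to 0.7. SDs at baseline and follow-up: not given, assumed equal (s) in the main calculation. All 20 per arm analysed, one follow-up.

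**Step 1: the two variances.** With one baseline and one follow-up, the time-by-arm interaction is algebraically the arm difference in mean change.
- Interaction: 2(1 − r) × s² × 2/n
- Baseline as covariate: (1 − r²) × s² × 2/n
- Ratio, interaction to adjusted: 2/(1 + r)

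**Step 2: results for n = 20.**

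| r | 2(1 − r) | 1 − r² | Ratio | Interval wider by | n per arm to match (20 × ratio) | Extra per arm |
|---|---|---|---|---|---|---|
| 0.3 | 1.40 | 0.91 | 1.538 | 24% | 30.8 | 10.8 |
| 0.5 | 1.00 | 0.75 | 1.333 | 15% (√1.333 = 1.155) | 26.7 | 6.7 |
| 0.7 | 0.60 | 0.51 | 1.176 | 8% (√1.176 = 1.085) | 23.5 | 3.5 |

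Rounded up, that is 11, 7 and 4 extra per arm. Counted from the 20 enrolled, the interaction is as precise as an adjusted analysis of 13, 15 or 17 per arm, a loss of 7, 5 or 3.

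An unadjusted follow-up comparison has variance factor 1. At r = 0.5 the interaction therefore only equals ignoring baseline altogether, and below 0.5 it does worse.

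**Step 3: cost of the covariate.** Allowing for the lost degree of freedom (factor 1 + 1/36) gives 9.9, 5.9 and 2.9 extra per arm. A simulation of 20,000 trials of 20 + 20 at each r gave 10.1, 5.9 and 3.0.

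**Step 4: does the direction depend on equal SDs?** Let the SDs be s0 at baseline and s1 at follow-up. Then

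(s0² + s1² − 2r·s0·s1) − s1²(1 − r²) = (s0 − r·s1)² ≥ 0.

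Apart from the degree of freedom, adjustment cannot lose. The size does depend on the SDs. With s0 half of s1, the extra need is 0.9, 0.0 and 1.6 per arm at r = 0.3, 0.5 and 0.7. With s0 at 1.25 times s1, it is 19.8, 15.0 and 11.9.

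**Step 5: other variations.** If 16 per arm are analysed, the extra need is 8.6, 5.3 and 2.8. For baseline against the mean of four follow-ups, with all correlations equal to r, the adjusted-to-interaction variance ratio is (1 + 4r)/5, and the extra need is 25.5, 13.3 and 6.3.

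**Step 6: chance imbalance.** The SD of the baseline difference between arms of 20 is √(2/20) = 0.32 of a baseline SD.

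**The case against.** The strongest reply is that this is an efficiency refinement for measures outside the main outcomes of a small pilot that plays down significance testing. Protocol section 3.3 makes feasibility, satisfaction and adherence primary. Satisfaction and attendance have no baseline value, and adherence is a yes/no composite. That stands, and it limits the scope.

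A second reply is that the analysed model is unclear. Delay discounting has two occasions and cannot fill five levels. A full five-level interaction has 4 degrees of freedom, so no single variance ratio describes it. The SAP's sentence about separate analyses at each follow-up sits uneasily with one 5 by 2 model. This stands for the size in repeated measures. Under separate analyses, the single-follow-up calculation applies to demand and craving too. For measures with one follow-up it applies on either reading.

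A reader might also infer more than the documents support:
- **That the planned estimate is biased.** It is not. Under randomisation the interaction contrast is unbiased; the over-correction is conditional on the imbalance observed. Adjustment removes the linear part of that imbalance.
- **That the gain reaches all the hypothesised BSM effects.** Time Spent On Activities has no scheduled follow-up. The repeated activities form (Protocol 12.2.16) rates helpfulness, not hours.
- **That the urine result would gain similarly.** The formula is for continuous measures, and the documents do not say how much intake buprenorphine results vary. If they vary little, there is little to adjust for.
- **That keeping baseline as an outcome is itself the error.** A longitudinal model with arm means constrained equal at baseline recovers essentially the same precision.

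**Conclusion.** The point holds for continuous measures with a baseline value: delay discounting, opioid demand, craving, EQ-5D-5L, and the substance-free activities rating if it is scored as a total. The planned interaction is a less efficient route to the arm effect than a baseline-adjusted comparison.

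That direction rests on algebra and holds for any SDs, apart from one degree of freedom. The size is conditional: roughly 4 to 11 more participants per arm, and intervals 8% to 24% wider, for r from 0.7 down to 0.3. It assumes equal SDs, one follow-up and 20 per arm analysed. The participant figure is the additional enrolment needed to match the adjusted analysis, not a number lost from the 20; that loss is 3 to 7. The change is worth making because it is nearly free and serves the pilot's stated aim, but the planned analysis is not invalid without it.

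**What to change.** In the SAP, for each continuous outcome with a baseline value, specify the CM-BSM difference at follow-up, with a confidence interval, from a model containing arm and the participant's own baseline value.

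For measures repeated at S1 to S4, use a mixed model with baseline as a covariate, or one that keeps baseline as an outcome with arm means constrained equal at that occasion. State which follow-up contrast is the one to be reported; this also settles the tension between separate analyses and a single five-level model.

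An intake urine covariate for the drug-screen outcome can be left out or made optional.

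The cost is one SAP sentence and one degree of freedom per model. No new data are needed.
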